IgA, IgG, and IgM levels		X				X ⁱ	X ⁱ								X		X					X
Urinalysis	X	X						X									X					X
Tuberculosis testing	X																					
Pregnancy ^j	X	X						X								X	X			X	X	
Anti-CCP	X																					
Rheumatoid factor	X																					

Page 2 of 2

AE = adverse event; BL = Baseline; CRP = C-Reactive Protein; EOI = End of Infusion; EOS = End of Study; ESR = Erythrocyte sedimentation rate; h = hour; HAQ-DI = Health Assessment Questionnaire – Disability Index; HBsAg = Hepatitis B surface antigen; Anti-HBc = Hepatitis B core antibody; HCV = Hepatitis C virus antibody; Ig = Immunoglobulin, PK = Pharmacokinetic; Scn = Screening; VAS = Visual analogue scale; Anti-CCP= Anti-cyclic citrullinated peptide antibody

^a The second dose will be administered at week 24 or earlier, ie, anytime from week 16 to week 24, in individual subjects, if necessary in the opinion of the Investigator. For subjects who receive retreatment before week 24, all week 24 and post-week-24 assessments will be moved up to the corresponding time point after treatment (eg, week 26 will be 2 weeks after retreatment, week 30 will be 6 weeks after retreatment, etc.). An infusion may be delayed up to 7 days to allow for recovery from infection.

^b Subjects early terminating study should perform week 48 procedures.

^c Historical radiograph performed within 3 months prior to first dose of IP may be used and does not need to be repeated at screening ([section 10.7](#) for details)

^d ABP 798/rituximab dosing to be administered after all other procedures are completed for each visit.

^e Subjective assessments will be the first procedures performed at the visit.

^f Includes any other lab tests required only for screening. Creatinine clearance calculation will be performed only at screening.

^g Either CRP or ESR is required at screening. CRP will be performed by central lab and results will be blinded to study sites. ESR will be performed by local laboratory.

^h PK sampling: day 1, predose, at EOI, and 3 and 6 hours postdose; day 2 (24 hours postdose); day 3 (48 hours postdose); day 15, predose, at EOI, and 3, 6, and 24 hours postdose (day 16), and 48 hours postdose (day 17). In addition, at week 4 (day 29), week 8 (day 57), week 12 (day 85), and predose week 24, week 26, and week 30, 48/EOS. Blood sampling for PK analysis during each return visit, including the EOS visit, will occur per the scheduled time point with tolerance collection

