10.9 Blood Samples for Pharmacokinetic Analysis

During treatment, a series of serum samples will be taken according to [Table 1](#). The exact times of blood sampling will be recorded.

Blood sampling for PK analysis during each return visit, including the EOS visit, will occur per the scheduled time point with tolerance collection windows as follows:

- predose day 1 = within 1 hour prior to dosing
- days 1 and 15 at EOI - infusion should be monitored to ensure collection of the PK sample within 10 minutes after the end of the infusion
- all other day 1 sampling times = \pm 10 minutes
- days 2 and 3 = \pm 3 hours
- predose day 15 = within 1 hour prior to dosing
- all other day 15 sampling time = \pm 10 minutes
- days 16 and 17 = \pm 3 hours
- weeks 4, 8, and 12 = \pm 2 days
- predose at weeks 24 and 26 = within 1 hour prior to dosing
- weeks 30 and 48 = \pm 2 days

Details of the procedures to be followed for sample collection, storage, and shipment will be documented in the Laboratory Manual.

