## 5.2 PHARMACOKINETIC

Pharmacokinetic parameters will be calculated from serum concentration-time data using noncompartmental analysis (NCA) methods using Phoenix WinNonLin® Version 6.4 or higher (Pharsight Corp, St. Louis, MO). The following PK parameters will be reported for serum rituximab and ABP 798, using actual elapsed sampling times:

Variable	Definition
$C_{max1}$	Maximum observed serum concentration following Dose 1 Infusion 1
$C_{max2}$	Maximum observed serum concentration following Dose 1 Infusion 2
$t_{max1}$	Time to which the maximum serum concentration was observed following Dose 1 Infusion 1
$t_{max2}$	Time to which the maximum serum concentration was observed following Dose 1 Infusion 2
TLST1	Time of last quantifiable concentration following Dose 1 Infusion 1

Sponsor: Amgen Inc.

Protocol No: 20130108

Statistical Analysis Plan

10-December-2018/ Version 2.0

CLST1	Last quantifiable concentration following Dose 1 Infusion 1 over first 14 days postdose (day 15)
AUC 0-14 day	Area under the serum concentration-time curve from time 0 on day 1 prior to the first infusion of the first dose to last quantifiable concentration associated with Dose 1 Infusion 1 over the first 14 days postdose (day 15)
TLST2	Time of last quantifiable concentration associated with Dose 1 Infusion 2
CLST2	Last quantifiable concentration after Dose 1 Infusion 2
AUC 0-12 wk	Area under the serum concentration-time curve from time 0 on day 1 prior to the first infusion of the first dose to last quantifiable concentration over 12-week profile
AUC inf	Area under the serum concentration-time curve from time 0 on day 1 prior to the first infusion of the first dose extrapolated to infinity; calculated as AUC last + CLST2/λ z , where AUC last is the AUC from time 0 to the last quantifiable concentration up to week 12 (i.e. AUC 0-12 wk )
t 1/2	Terminal elimination half-life determined from time 0 to Week 12 profile; calculated as ln(2)/ λ z
λ z	Terminal elimination rate constant
CL	Clearance
AUMC	Area under the first moment curve
MRT	Mean residence time; calculated as AUMC inf /AUC inf – TI /2, where TI represents infusion duration and AUMC inf is the area under the moment curve from the time of first dosing extrapolated to infinity.
AUC 0-12 wk /AUC inf	calculated as AUC 0-12 wk /AUC inf

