AUC% extrap	Percent of AUC extrapolated to infinity in AUC inf

Following administration, Cmax, tmax, CLST and TLST will be obtained directly from the experimental observations. If multiple maxima occur at equal concentrations after an infusion, the first temporal value will be used.

AUC0-14 day, AUC0-12 wk and AUCinf will be estimated using the linear trapezoidal rule.

Values of AUC0-14 day and Cmax associated with Dose 1 Infusion 2 will be listed but excluded from descriptive statistics and statistical analysis if the time of the last concentration following Dose 1 Infusion 1 is outside ± 2 day window around Day 15.

Sponsor: Amgen Inc.

Statistical Analysis Plan

Protocol No: 20130108

10-December-2018/ Version 2.0

Values of  $AUC_{0-12\text{ wk}}$  will be listed but excluded from descriptive statistics and statistical analysis if the time of the last concentration following Dose 1 Infusion 2 is outside  $\pm 2$  week window around Week 12.

The terminal half-life,  $t_{1/2}$ , where determined, will be calculated as  $\ln(2)/\lambda_z$ . The number of data points included in the regression will be determined by visual inspection, but a minimum of three data points in the terminal phase, excluding  $C_{\max}$ , will be required to estimate  $\lambda_z$ .  $\lambda_z$  values (and consequently  $t_{1/2}$  and  $AUC_{\text{inf}}$  values) will be considered unreliable estimates if the time period over which an individual  $\lambda_z$  was required is less than twice the resultant  $t_{1/2}$  or the adjusted coefficient of determination 'Rsq' is less than or equal to 0.8. Additional exclusions of PK parameters, if any, will be described in the CSR.

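### A missing day-15 predose sample alone removes a fully observed primary Cmax value, because SAP 5.2 ties exclusion of Cmax after infusion 2 to the last sample after infusion 1

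*SAP*

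**What the plan says.** SAP 4.1 names AUCinf and Cmax after the second infusion of the first dose as the primary PK endpoints. SAP 5.2 defines the latter (Cmax2) as "Maximum observed serum concentration following Dose 1 Infusion 2" and says that Cmax values "will be obtained directly from the experimental observations".

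The same section then sets one exclusion rule for two parameters, AUC0-14day and Cmax2. Both stay in the listings but are left out of every summary and comparison "if the time of the last concentration following Dose 1 Infusion 1 is outside" a window of two days either side of day 15.

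Three parts of the protocol bear on how the rule works:

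- Table 1, footnote h (Protocol 8.6.1.1) schedules PK samples on days 1, 2 and 3, and then nothing until the day-15 predose sample.
- Protocol 10.9 ties that sample to the infusion: "predose day 15 = within 1 hour prior to dosing".
- Table 1, footnote a, whose marker stands on the dosing row as well as on week 24, says: "An infusion may be delayed up to 7 days to allow for recovery from infection".

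The PK parameter analysis set (SAP 6.5) requires a complete day-1 dose and a usable concentration profile. It requires neither a day-15 predose sample nor an on-time second infusion.

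**The concern.** The rule suits AUC0-14day, which cannot be computed properly without a concentration near day 15. Cmax2 is different: no sample from before infusion 2 enters it. If the predose sample is missing, Cmax2 is exactly what it would have been with the sample present, yet the rule removes it. At stake is a primary value discarded for a sampling fault that has no bearing on it.

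Cmax2 also enters the rituximab (US) versus rituximab (EU) comparison, which decides whether the two reference arms are pooled for the efficacy analysis (SAP 9.5.2 and 9.7). The values that are kept therefore matter beyond the two ABP 798 comparisons.

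**Working it through.** **1. Applying the rule to the schedule.** The window is day 15 ± 2, that is days 13 to 17.

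| Situation | Last concentration after infusion 1 | Cmax2 |
|---|---|---|
| Predose taken, infusion on day 15 | day 15 | kept |
| Predose missed, all infusion 2 samples on time | day 3 (15 − 3 = 12 days early) | excluded |
| Infusion delayed 1–2 days, predose taken | day 16–17 | kept |
| Infusion delayed 3–7 days, predose taken | day 18–22 | excluded |

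**2. Whether anything restores the value.** SAP 9.5.2 lists three kinds of sensitivity analysis: the per-protocol PK parameter set, which is a subset of the primary set; the primary set without covariates; and the ADA-negative subgroups. None brings an excluded Cmax2 back.

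**3. The plan's own power figure.** Inputs from Protocol 12.2: 300 subjects randomized 1:1:1, 15% dropout by week 24, CV 40%, true GMR 1, limits 0.8 to 1.25, significance level 0.05 per comparison.

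- n per arm = 100 × 0.85 = 85.
- Log-scale SD = √ln(1 + 0.4²) = √ln 1.16 = 0.385.
- SE of the log ratio = 0.385 × √(2/85) = 0.0591.
- Power (normal) = 2Φ(ln 1.25/SE − 1.645) − 1 = 2Φ(3.776 − 1.645) − 1 = 96.7%. With the t distribution it is 96.6%.

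The stated figure of more than 90% is reproduced for a single comparison.

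**4. Power after exclusions (t-based, per comparison).** The documents give no rate of missing predose samples, so the removed share is an assumption.

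| Cmax2 values removed | n per arm | Power |
|---|---|---|
| 0% | 85 | 96.6% |
| 5% | 81 | 95.7% |
| 10% | 77 | 94.7% |
| 20% | 68 | 91.4% |

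Power first drops below 90% under 66 per arm, which needs more than 1 − 66/85 = 22% of values removed. If both ABP 798 comparisons on Cmax2 must succeed, simulated power is 93.9% with none removed, 91.9% at 80 per arm and about 90% at 76.

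**5. Effect of a delay on Cmax2.** The documents give no half-life. Assume one compartment and a terminal half-life of 16 to 25 days, with k = ln 2/half-life. For a delay of d days the ratio of Cmax2 to its on-time value is (1 + e^(−k(14+d)))/(1 + e^(−14k)).

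- d = 7, half-life 16 days: 1.403/1.545 = 0.908.
- d = 7, half-life 25 days: 1.559/1.678 = 0.929.
- d = 3: 0.957 and 0.968.

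A 7-day delay thus lowers Cmax2 by about 7–9%, and a 3-day delay by about 3–4%. A missed predose sample changes it by 0%.

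**The case against.** The strongest defence is that the predose sample, taken within an hour of dosing, is a close proxy for the time of infusion 2. A window of ± 2 days then standardises the two-week interval, and carry-over from infusion 1 does change Cmax2. This stands as a reason for some timing rule, and it makes excluding delays of 3–7 days defensible. It fails where the sample is missing, because day 3 then says nothing about when infusion 2 was given.

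A missed predose sample should also be uncommon. Protocol 9.5 lists it among the procedures before the infusion, and Protocol 8.5.1 places dosing after all other procedures. The 5–10% above may therefore be too high. Starting from 85 per arm is also cautious, since Cmax2 is observed by about day 17, before all the dropout expected by week 24; at 100, 95 and 90 per arm, power is 98.5%, 98.0% and 97.4%. Both points stand and limit the size of the problem.

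A reader might infer that an incomplete second infusion goes unscreened while harmless cases are dropped. The documents do not support that: SAP 9.5.1 and 9.5.2 let blinded review declare samples or profiles not evaluable after an incomplete infusion, and 9.5.2 extends this to long interruptions and unusually long infusions. The wording is discretionary, but the case is covered.

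A reader might also infer bias between arms. The rule is pre-specified, takes no account of arm in a double-blind trial, and keeps the excluded values in the listings. Nothing in the documents suggests that missed samples or delays would differ by arm.

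**Conclusion.** The concern holds for the missing predose sample. As written, SAP 5.2 removes a fully observed primary value for a reason that cannot affect it, and no planned analysis restores it.

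The loss of precision is small. If 5–10% of values were removed, power per comparison would go from 96.6% to about 95.7–94.7%, so the stated power of more than 90% still holds. This rests on the plan's own CV, GMR and dropout, and on a loss rate the documents do not give. The reason to act is retention of valid primary data.

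Whether delays of 3–7 days belong in the primary analysis is a judgement, and delays of 1–2 days are already kept. Still, a subject can follow the protocol's delay allowance and lose a primary value under the SAP, so the two passages must be reconciled.

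**What to change.** In SAP 5.2:

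- Apply the window on the last concentration after infusion 1 to AUC0-14day only.
- Base any timing exclusion of Cmax2 on the actual time of infusion 2 and on having an evaluable sample around its end, so that a missing predose sample alone never excludes Cmax2. SAP 5.1 already anchors the post-infusion day-15 PK samples to the actual stop time of infusion 2.
- State whether Cmax2 after a delay of 3–7 days is kept in or dropped from the primary analysis, and reconcile that choice with Table 1, footnote a.

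In SAP 9.5.2, add a sensitivity analysis of all observed Cmax2 values.

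The cost is one reworded sentence and one extra table. If delayed infusions are kept, a few values with slightly lower carry-over add a little variability, small against the assumed CV of 40%.

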### 9.5.2 Pharmacokinetic Parameters

PK parameters for ABP 798 and rituximab will be estimated using noncompartmental analysis methods with Phoenix WinNonlin® Version 6.4 or higher (Pharsight Corp., St. Louis, MO).

In the event that a subject does not receive the full protocol-specified infusion, subsequent PK samples may be considered not evaluable and thus certain PK parameters may not be reportable. In addition, if the full protocol-specified dose was given but there was a long dose interruption or unusually long infusion duration that was deemed to impact PK, the PK profile may be considered not evaluable. The subject exclusion from the PK parameter analysis set will be determined based on a blinded data review prior to unblinding for the final analysis. Any such exclusion will be clearly listed in the CSR along with justification for exclusion.

Pharmacokinetic parameters will be listed by subject and summarized descriptively by treatment for the PK parameter analysis set. The following descriptive statistics will be provided: n, arithmetic mean, SD, Q1, Q3, minimum, median and maximum. Only n, median, Q1, Q3, minimum and maximum will be reported for  $t_{max}$ . In addition, geometric mean, and geometric CV will be calculated for  $AUC_{inf}$ ,  $AUC_{0-14\ day}$ ,  $AUC_{0-12\ wk}$ ,  $C_{max}$ ,  $CLST2$ ,  $t_{1/2}$ ,  $\lambda z$ , CL, MRT,  $AUC\%extrap$  and  $AUC_{last}/AUC_{inf}$ .

The serum PK parameters will be estimated from the individual concentration data for all subjects in the PK parameter analysis set. In estimating the PK parameters, BQL values at

Sponsor: Amgen Inc.

Statistical Analysis Plan

Protocol No: 20130108

10-December-2018/ Version 2.0

the beginning of the profile will be set to zero. BQL values that occur after the first quantifiable point will be considered missing. Actual sampling times will be used in all computations.

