## PRIMARY STATISTICAL ANALYSIS

The PK similarity will be demonstrated by comparing the 90% CI for the GMR of test (ABP 798)-to-reference (US-licensed rituximab or EU-authorized rituximab) and rituximab [US] to rituximab [EU] for  $AUC_{inf}$  and for  $C_{max}$  following the second infusion of the first dose with the bounds of 0.8 to 1.25. Point estimates and CIs for the GMR will be estimated from an analysis of covariance model using the PK parameter analysis set. For  $AUC_{inf}$  and  $C_{max}$  after second infusion of the first dose, the point estimates and 90% CIs for the GMR for will be estimated using an analysis of covariance model adjusted for weight and geographic region. A sample SAS code for PROC MIXED is displayed below:

CCI

The geometric least square means for each treatment will be presented. The ratios of the geometric means for the comparison of the test treatment to the reference treatment will be obtained by exponentiating the difference of the means on the natural log scale. The CIs will be obtained by exponentiating the CI for the difference between the means on the log scale. Plots of the ratio of geometric means and 90% CI will be displayed.

Additionally, the similarity between PK endpoints of rituximab (US) and rituximab (EU) will be evaluated as well. The GMRs and 90% CIs will be generated for other PK endpoints:  $AUC_{0-14\ day}$ ,  $AUC_{0-12\ wk}$ , and  $C_{max}$  after the first infusion of the first dose by using the same methods as stated above.

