## SENSITIVITY ANALYSES

A sensitivity analysis of all PK parameters will be analyzed similarly to the primary statistical analysis using the PP PK parameter analysis set.

In addition, the following sensitivity analyses will be performed on the PK parameter analysis set:

- The point estimates and CIs for the GMR will be estimated using a model similar to the primary statistical analysis model but excluding all covariates.
- The point estimates and CIs for the GMR will be estimated using the primary statistical analysis model for the subgroups of subjects with negative binding ADA status and negative neutralizing ADA status during first dose period.

Sponsor: Amgen Inc.

Statistical Analysis Plan

Protocol No: 20130108

10-December-2018/ Version 2.0

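### The window rule for the secondary endpoint AUC0-12wk, on its likelier reading, drops subjects sampled on time but below quantification at week 12, so exclusion depends on the subject's own elimination

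*SAP*

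**What the plan says.** SAP section 5.2 lists AUC0-12wk but leaves it out of descriptive statistics and statistical analysis "if the time of the last concentration following Dose 1 Infusion 2 is outside" a window of two weeks either side of week 12 ("week window around Week 12"). Three other statements decide what that means in practice.

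- The parameter table in SAP section 5.2 integrates AUC0-12wk "to last quantifiable concentration over 12-week profile", and defines TLST2 as "Time of last quantifiable concentration associated with Dose 1 Infusion 2".
- SAP section 9.5.2 says: "BQL values that occur after the first quantifiable point will be considered missing".
- The sampling footnote to Table 1 (Protocol section 8.6.1.1) schedules later samples at "week 4 (day 29), week 8 (day 57), week 12 (day 85), and predose week 24". Nothing is scheduled between weeks 8 and 12.

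AUC0-12wk is a secondary PK endpoint (SAP section 4.2.1). SAP section 9.5.2 gives it formal comparisons: "The GMRs and 90% CIs will be generated for other PK endpoints", AUC0-12wk among them. The co-primary endpoints are AUCinf and Cmax after the second infusion.

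**The concern.** A window on sampling time is a sensible guard against profiles with a missing or badly mistimed week-12 sample. Read with the other definitions, this one also catches a compliant subject whose week-12 sample was drawn on time and came back BQL. What triggers that exclusion is fast elimination, which is part of what the endpoint measures.

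If the two products are eliminated at different rates, more subjects leave the faster arm, and those who leave have the lowest exposure. The remaining groups look more alike than the randomised groups, and their spread is smaller. Both effects favour a 90% CI inside 0.80 to 1.25. At stake is whether the AUC0-12wk comparison can be relied on as supportive evidence of similar exposure.

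**Working it through.** **1. The plan's own figure.** The documents give no figure for this rule. The nearest is the power statement for the primary PK endpoints (Protocol section 12.2): above 90%, with CV 40%, true GMR 1, margin 0.8 to 1.25, 100 per arm and 15% dropout.

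- Log-SD = sqrt(ln(1 + 0.40²)) = 0.385.
- SE with 85 per arm = 0.385 × sqrt(2/85) = 0.0591.
- Two one-sided tests: ln(1.25)/0.0591 − 1.654 = 2.12, giving power of 96.5%. With 100 per arm it is 98.5%.

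The stated power is reproduced. The same log-SD and 85 per arm are used below.

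**2. Who is excluded.** Week 12 is day 85, so the window is days 71 to 99. Week 8 is day 57, and with its 2-day tolerance day 59 at the latest, which is 12 days before the window opens. A subject BQL at week 12 therefore cannot meet the rule if the last concentration means the last quantifiable one.

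**3. How complete that subject's AUC is.** Illustration with assumed values: one compartment, two equal doses 14 days apart, half-life 9 days, quantification limit 1% of a single-dose peak.

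- Week 12 (70 and 84 days after the infusions): 2^(−70/9) + 2^(−84/9) = 0.0046 + 0.0015 = 0.6% of peak, so BQL.
- Week 8 (42 and 56 days): 2^(−42/9) + 2^(−56/9) = 0.0394 + 0.0134 = 5.3% of peak, so quantifiable.
- AUC to week 8 over AUC to week 12 = (1 − 0.0528/2)/(1 − 0.0061/2) = 0.9736/0.9969 = 0.977.

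Across simulated subjects of this kind the fraction was about 97 to 99%. Little exposure is missing from the value that is dropped.

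**4. Effect on the ratio.** Simulation with a one-compartment model, log-SD 0.385 for clearance and 0.2 for volume, half-life 12 or 18 days, and the limit set so that a chosen share of reference subjects is BQL at week 12. Half-life, volume variability and limit are assumptions; none is in the documents.

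With clearance raised so that the AUCinf GMR is 0.80, and 5% of reference subjects BQL, the rule drops 5% of the reference arm and 13% of the test arm. The AUC0-12wk GMR moves from 0.812 to 0.852 (12 days) or from 0.827 to 0.868 (18 days). In the 12-day case the log-SD of the faster arm falls from 0.367 to 0.306.

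With clearance set so that the all-subject AUC0-12wk GMR is exactly 0.80, and 85 per arm before exclusions, the chance of wrongly passing is 0.048 to 0.050 if every subject is kept. Under the rule:

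| Reference BQL at week 12 | Test arm dropped | GMR under the rule | Chance of passing 0.80–1.25 |
|---|---|---|---|
| 0.5% | 2.2–2.5% | 0.811–0.812 | 0.08–0.09 |
| 2% | 6.8–7.6% | 0.826–0.829 | 0.15–0.19 |
| 5% | 14–15% | 0.843–0.849 | 0.26–0.36 |
| 10% | 24–25% | 0.861–0.869 | 0.43–0.58 |
| 20% | 39–40% | 0.884–0.895 | 0.65–0.82 |

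**5. Where it does not bite.** With equal clearance the GMR stays at 1.00 for every BQL share tried. A 20% difference in amount delivered, with clearance equal, is barely affected (0.800 to 0.804 at 5% BQL, 12 days).

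**The case against.** **The reading is inferred.** The exclusion sentence refers to the last concentration, without the word quantifiable and without naming TLST2. The parallel sentence for day 15 looks like a check on sampling time. If the sponsor means the last sample taken, an on-time BQL sample satisfies the rule and the problem disappears. This stands as a real ambiguity. The definitions of AUC0-12wk and TLST2 and the BQL rule make the other reading likelier, and the sponsor's intent would still need to be written down.

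**The primary conclusion is not reached.** A reader might infer that the rule could carry the trial to a false finding of PK similarity. The documents do not support that. The sentence removes only AUC0-12wk; AUCinf is still formed from the AUC to the last quantifiable concentration plus an extrapolated tail. For a subject last quantifiable at week 8, days 17 to 57 span 40 days, enough for the reliability criterion of two half-lives whenever the half-life is 20 days or less. In the table's scenarios the true AUCinf GMR is 0.769 to 0.791, already outside the margin. With SE 0.0591, (ln(0.791/0.80)/0.0591) − 1.654 = −1.85, a pass probability of about 3%; at 0.769 it is about 1%. This objection stands in full.

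**A difference would remain visible elsewhere.** The excluded values are listed, and clearance and half-life are summarised by treatment. True, but the formal AUC0-12wk comparison would still be biased, and none of the planned sensitivity analyses restores the values. The first is: "A sensitivity analysis of all PK parameters will be analyzed similarly to the primary statistical analysis using the PP PK parameter analysis set". The others are a model without covariates and the antidrug-antibody-negative subgroups.

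**The size is assumed.** This also stands. A reader might infer that antibody-driven fast clearance is being hidden. If 10% of test subjects cleared three times faster, the GMR would move from 0.90 to 0.99 at 5% reference BQL, but the documents give no antibody rate or clearance effect, so this is only an illustration.

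**Conclusion.** The concern holds for the supportive AUC0-12wk comparison. On the likelier reading, exclusion depends on the subject's own elimination. If elimination differs between arms, the GMR is pulled towards 1 and its CI is narrowed. If elimination is equal, as the planning assumption of a GMR of 1 implies, the ratio is unbiased and the cost is lost subjects.

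The size depends on the share of subjects BQL at week 12, which cannot be obtained from the documents. With half-lives of 12 to 18 days and a clearance difference that puts the GMR near 0.80, the shift is about 0.01 if 0.5% of reference subjects are BQL and about 0.04 to 0.05 if 5% are. The sentence does not exclude the co-primary AUCinf or Cmax after the second infusion, and this point makes no claim about them. The rule should be corrected because it can bias a reported GMR and CI and the repair is simple.

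**What to change.** Reword the sentence in SAP section 5.2 so that the window applies to the time the week-12 sample was drawn. Exclude AUC0-12wk only when no week-12 sample was taken within the window. If one was taken and is BQL, keep the AUC to the last quantifiable concentration. In the 5% BQL example of step 4 this leaves the GMR at about 0.81 (12 days) or 0.83 (18 days), instead of 0.85 or 0.87.

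Report the number of AUC0-12wk values excluded by arm and by reason (sample missing, sample mistimed), with the number of week-12 samples that were BQL in each arm. The reader can then see whether the question arose at all.

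The cost is one SAP sentence and one small table, made before unblinding. It needs no new data and does not change the primary analysis, and the guard against missing or mistimed samples is kept.

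### If the products differ in clearance, the linear trapezoidal rule and the λz reliability rule in SAP 5.2 both pull the primary AUCinf ratio toward 1, and no planned sensitivity analysis would show it

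*SAP*

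**What the plan says.** AUCinf and Cmax after the second infusion of the first dose are the primary PK endpoints (SAP 4.1; Protocol 8.6.1.1). SAP 5.2 settles three things about AUCinf:

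- **Integration.** The three AUCs, including AUCinf, "will be estimated using the linear trapezoidal rule". The observed part of AUCinf "is the AUC from time 0 to the last quantifiable concentration up to week 12", so the profile stops at day 85.
- **Regression.** "The number of data points included in the regression will be determined by visual inspection", with at least three points excluding Cmax.
- **Reliability.** λz, and with it t1/2 and AUCinf, "will be considered unreliable estimates if the time period over which an individual" λz was fitted is under twice the resulting half-life, or if adjusted R² is 0.8 or lower.

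The consequence of the reliability flag is not stated. The following sentence reads "Additional exclusions of PK parameters, if any, will be described in the CSR", which implies that flagged values have already been excluded. For AUC0-12 wk, by contrast, values "will be listed but excluded from descriptive statistics and statistical analysis if the time of the last concentration" lies outside a window; AUC0-14 day and second-infusion Cmax get the same explicit treatment.

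Under SAP 9.5.2 (Primary Statistical Analysis), the ratio and its 90% CI "will be estimated using an analysis of covariance model adjusted for weight and geographic region", for both ABP 798 comparisons and for rituximab (US) versus (EU). The PK sensitivity analyses are the per-protocol PK set, a model without covariates, and the subgroups negative for binding or neutralizing antibodies.

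**The concern.** In an equivalence test, a bias toward 1 raises the chance of concluding similarity when the true ratio lies at or beyond the margin. Both features can do this when clearance differs between products.

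- The span criterion removes long half-lives. With lower clearance, half-life and AUCinf rise together, so more subjects leave the higher-exposure arm.
- Linear interpolation over a 28-day exponential decline overstates the area, and does so more in the faster-clearing arm.

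Every listed sensitivity analysis would inherit both features. The same AUCinf values feed the US–EU comparison, which decides under SAP 9.7 whether the two reference arms are pooled for the DAS28-CRP assessment.

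**Working it through.** **1. The plan's own figure.** Protocol 12.2 gives CV 40%, true ratio 1, bounds 0.8–1.25, 15% dropout and 300 subjects at 1:1:1. The log SD is √ln(1 + 0.40²) = 0.385, and 100 × 0.85 = 85 per arm. Two one-sided 5% tests then have 96.6% power for one comparison, consistent with the stated figure of more than 90%. That figure is not in dispute.

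**2. What the span criterion flags.** A span below 2 × t1/2 is the same as t1/2 > span/2. Protocol Table 1 (footnote h) schedules samples on days 16, 17, 29, 57 and 85 after the second infusion.
- Days 29–85: span 56 days, cut-off 28 days.
- Days 17–85: span 68 days, cut-off 34 days.

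The cut-off therefore depends on points chosen by eye.

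**3. Selection on exposure.** In a one-compartment model AUCinf = dose/CL and t1/2 = ln 2 × V/CL. Assume median t1/2 18 days, CL CV 40%, V CV 15%, uncorrelated. The log SD of t1/2 is √(ln 1.16 + ln 1.0225) = 0.413.
- Reference: ln(28/18)/0.413 = 1.07, so 14.2% flagged, about 12 of 85.
- Test with AUCinf 1.25 times as high through clearance (t1/2 22.5 days): ln(28/22.5)/0.413 = 0.53, so 29.8% flagged, about 25 of 85.

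Across the settings in step 6, the counts at 18 days are about 1–12 (reference) and 7–25 (1.25 arm).

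**4. Linear rule.** Over an interval Δ of exponential decline with x = ln 2 × Δ/t1/2, linear area divided by true area is (x/2)·coth(x/2). For Δ = 28 days (days 29–57 and 57–85):
- t1/2 18 days: x = 1.078, factor 1.095.
- t1/2 22.5 days: x = 0.863, factor 1.061.

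Within those intervals the ratio is multiplied by 1.061/1.095 = 0.969, toward 1. At 10 versus 12.5 days the factors are 1.296 and 1.193, and the multiplier is 0.921.

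**5. AUC0-12 wk as a safeguard.** It needs no λz, but it is truncated. Treating infusions as instantaneous, the share beyond day 85 is the mean of exp(−84k) and exp(−70k), with k = ln 2/t1/2. At 18 days this is (0.039 + 0.068)/2 = 0.053; at 22.5 days it is (0.075 + 0.116)/2 = 0.095. A true AUCinf ratio of 1.25 becomes 1.25 × 0.905/0.947 = 1.19 before the linear rule pulls it further toward 1.

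**6. Size, illustration only.** Assumptions: one compartment; the protocol's sampling to day 85; 4-hour infusions; 10% residual error; CL CV 30% or 40%, each with V CV 15% (uncorrelated) or 30% (correlation 0.5); last 3 or last 5 points for λz; 85 per arm; true ratio 0.80 or 1.25 through clearance. Chance that a single AUCinf comparison passes, nominal 5%:

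| Median t1/2 | 10 d | 14 d | 18 d | 22 d |
|---|---|---|---|---|
| Log-down, all kept | 4–6% | 4–6% | 4–6% | 4–6% |
| Linear, all kept | 11–18% | 9–14% | 8–12% | 6–11% |
| Linear plus exclusion | 12–19% | 11–34% | 13–59% | 17–71% |

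The last row is the plan as naturally read. At 10 days nearly all of the excess comes from the linear rule. At 18–22 days exclusion usually contributes more.

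**The case against.** **Conditional on facts outside the documents.** No half-life is given, and the 40% CV is for the PK endpoints, not for clearance. A proportional exposure difference leaves the ratio unchanged. A volume difference moves it away from 1, which makes the rule conservative. A reader might infer that the planned AUCinf analysis is biased toward similarity in general; the documents do not support that.

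**Single-comparison rates overstate the risk to the overall decision.** This stands. Similarity is assessed on two endpoints against two references. For exclusion without the linear rule, the joint rates at 10 / 14 / 18 / 22 days were 1–2 / 1–9 / 3–31 / 4–44% with CL CV 40%, and 1–2 / 1–2 / 1–7 / 2–13% with both CVs at 30%.

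**The benchmark is favourable.** Log-down is nearly exact for mono-exponential decline. In an assumed two-compartment model, log-down with all values kept itself passes 6–14%, against 9–38% for exclusion at 18 days. The contrast narrows, and the low ends are close.

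**The handling is stated well enough.** Partly so. A reader might infer that the SAP leaves flagged values undefined, but its reference to further exclusions points to removal. The model code is redacted and the table shells are a separate document, so the handling may be explicit there. The wording alone would be a minor matter.

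**Safeguards exist.** SAP 9.5.2 says "Pharmacokinetic parameters will be listed by subject and summarized descriptively by treatment for the PK parameter analysis set", with n and the extrapolated percentage included. These would show a shortfall in numbers, but not its effect on the AUCinf ratio.

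**The rule has a purpose.** Flagged values rest more on extrapolation. In simulation, a median of 17–26% of their AUCinf was extrapolated (90th percentile 22–36%), and they averaged 1–4% above truth. They would be less dependable in irregular or antibody-affected profiles. This is why no primary handling is prescribed here.

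**Conclusion.** The point holds in conditional form and should be fixed, with medium confidence. If the products differ through clearance, the linear rule and the exclusion of flagged values both move the AUCinf ratio toward 1, and no planned sensitivity analysis shows either effect. At the margin, the chance that one AUCinf comparison passes rises from about 5% to roughly 12–19% at a 10-day median half-life and 13–59% at 18 days. These rates rest on the assumed model, variability and half-life in the working. The direction follows from the sampling days and the SAP's rules once a clearance difference is assumed.

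A reader might go further and infer that a similarity finding from this trial would be unsound, or that the stated power is wrong. Neither follows: nothing in the documents indicates a clearance difference or a long half-life, and the power figure reproduces.

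**What to change.** Before unblinding for the final analysis:

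1. Calculate AUC by linear-up/log-down, or at least add it as a sensitivity analysis.
2. State in SAP 5.2 whether AUCinf values that fail the λz criteria enter the primary model. Pre-specify the opposite handling as a sensitivity analysis: all estimable values kept if exclusion is primary, or flagged values excluded if retention is primary. Run it for ABP 798 versus each reference and for rituximab (US) versus (EU).

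Which handling is primary is a trade-off for the sponsor, because retained flagged values carry a larger extrapolated share. The cost is a few sentences, one software setting and a few extra model runs. No new data are needed.
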